2.3.2 Known Potential Benefits

Immediate benefits for participants in the intervention arm are that participants may advance their understanding of the benefits of sleep and their metabolic risk and sleep health profile may improve. We have preliminary evidence demonstrating the effectiveness of this sleep intervention for improving sleep health (unpublished data). Others have demonstrated improvements in insulin sensitivity in normoglycemic adults following a sleep extension intervention⁷⁶. At the end of their participation in the study, participants in the intervention and the control arms will receive a study report from the research team that will include the results from their continuous glucose monitoring and sleep assessments with an explanation of the results and recommendations for improvement.

Long range potential benefits are that participants may gain some satisfaction that their participation will advance our understanding of the relationship between sleep and T2DM risk that may someday improve preventative efforts. Improving sleep in short sleeping adults may contribute to improved health in the long run.

3 Objectives and Purpose

The overall objective of this application is to test and compare the effects of a sleep intervention versus a control condition on blood glucose in short sleeping adults with prediabetes in a randomized clinical trial. The effect on changes in blood glucose relative to baseline will be established and compared across arms. The central hypothesis is that the sleep intervention will significantly improve glycemic control compared to the control intervention.

CONFIDENTIAL

This material is the property of the NYU School of Medicine and NYU Langone Health. Do not disclose or use except as authorized in writing by the study sponsor
Behavioral Intervention Template Version: 11 January 2019

3.1 Primary Objective

The primary objective is to determine the effect of a personalized sleep intervention on glycemic control. Our hypothesis is that the sleep intervention participants will have a lower percentage of time glucose is $\geq 140\text{mg/dL}$ compared to the control intervention participants after 8-weeks of treatment.

3.2 Secondary Objectives (if applicable)

The secondary objective is to determine the effect of a personalized sleep intervention on glycemic variability. Our hypothesis is that the sleep intervention participants will have a less glycemic variability compared to the control intervention participants after 8-weeks of treatment.

4 Study Design and Endpoints

4.1 Description of Study Design

This study is a phase 1, single center, single blind, parallel design randomized clinical trial. There will be two arms: 1) the sleep intervention arm and 2) the control arm. The sleep intervention arm will receive a personalized sleep intervention based on CBT-I that aims to extend sleep duration, improve sleep regularity, sleep efficiency, and sleep quality, as well as advance sleep timing. The sleep intervention arm will also receive 2019 American Diabetes Association (ADA) Standards of Medical Care recommendations for physical activity and nutrition in adults with prediabetes. The control arm will receive a time and attention matched lifestyle intervention recommendations according to ADA Standard of Medical Care for physical activity and nutrition. Generic sleep recommendations will also be included.

4.2 Study Endpoints

4.2.1 Primary Study Endpoints

The primary outcome will be the percent time glucose is $\geq 140\text{mg/dL}$, estimated from 7 days of continuous glucose monitoring. The percent time glucose is $\geq 140\text{mg/dL}$ was chosen as the primary endpoint because this variable is linked to postprandial glucose levels which when elevated uniquely predict oxidative stress⁸⁵⁻⁸⁷, macro and micro-vascular complications^{88,89}, and greater T2DM risk⁹⁰ in adults with prediabetes. Moreover the percent time glucose is $\geq 140\text{mg/dL}$, has been identified as one of the earliest indicators of T2DM risk⁹¹ and significant differences in the percent time glucose is $\geq 140\text{mg/dL}$ have been reported between people with and without prediabetes⁹¹. Continuous glucose monitoring results are validated measures to estimate glycemic control because continuous glucose monitoring data have been validated with blood glucose lab analyses ($r=0.95$)⁹².

4.2.2 Secondary Study Endpoints

Glucose variability estimated from continuous glucose monitoring will be a secondary study endpoint because this variable has also been associated with oxidative stress⁸⁵⁻⁸⁷, macro and micro-vascular complications^{88,89}.

4.2.3 Exploratory Endpoints

Exploratory endpoints will be diet quality, specifically percent carbohydrate and percent fat intake estimated from the ASA 24 diet recall, as well as physical activity estimated from the International Physical Activity Questionnaire (short form).

5 Study Enrollment and Withdrawal

5.1 Inclusion Criteria

In order to be eligible to participate in this study, an individual must meet all of the following criteria:

1. ≥ 21 years old and < 65 years old.

CONFIDENTIAL

This material is the property of the NYU School of Medicine and NYU Langone Health. Do not disclose or use except as authorized in writing by the study sponsor
Behavioral Intervention Template Version: 11 January 2019

2. HbA1c \geq 5.7% and $<$ 6.5% or taking Metformin or Glucophage. Individuals with a HbA1c in this range have been identified as being at greatest risk for progressing to T2DM and for developing microvasculature complications. This will also ensure that those recruited have prediabetes.
3. \leq 6.0 hours actigraphy-estimated sleep.
4. English speaking. Participants will need to demonstrate adequate English comprehension (assessed during informed consent). This is because the Sleep Environment Survey (used at baseline) has not been validated in other languages.

5.2 Exclusion Criteria

An individual who meets any of the following criteria will be excluded from participation in this study:

1. Diagnosis of T2DM or taking insulin or oral hypoglycemic medications (other than Metformin or Glucophage). The diagnosis of T2DM and treatment with anti-diabetic agents will confound continuous glucose monitoring assessments. Individuals taking metformin alone will not be excluded as metformin is frequently prescribed for prediabetes.
2. Pregnancy/lactation. Pregnancy and lactation can disrupt habitual sleep patterns and our primary interest is in recruiting individuals with habitual short sleep. Additionally, hormonal changes during pregnancy increase insulin resistance and may confound continuous glucose monitoring results⁹³.
3. Current chemotherapy treatments. Current chemotherapy treatments may contribute to fatigue and alter habitual sleep patterns⁹⁴.
4. Alcohol abuse/dependence may interfere with habitual sleep and limit the individual's ability to adhere to the sleep interventions. Alcohol abuse will be assessed with the Alcohol Use Disorders Identification Test (a measure that has demonstrated good reliability and validity). Individuals with scores > 15 (men) or > 13 (women) will be excluded⁹⁵.
5. Recent or planned night shift work (previous 2 months or during the intervention period) or trans-meridian travel > 1 hour time zone difference during the RECR previous 4 weeks or during the intervention period. Shift work and trans-meridian travel of > 1 hour may disrupt habitual sleep and limit the individual's ability to adhere to the sleep interventions.
6. Sleep disorders (other than OSA discussed above and insomnia symptoms). Specific sleep disorders will be assessed with selected questions from the Sleep Disorders Symptom Checklist-(SDS-CL-25) that screens for narcolepsy in questions 18-20 (summed average score ≥ 3), restless legs syndrome in questions 15-17 (summed average score ≥ 3), and parasomnias in question 23 because these sleep disorders may interfere with the individual's ability to adhere to the sleep intervention.
7. Chronic use of sleep-promoting medications (self-reported) defined as taking a sleep-promoting medication ≥ 3 nights per week. Chronic use of sleep medication may interfere with sleep patterns and limit the participant's ability to take part in the sleep interventions.
8. Unstable medical illness or health condition that may interfere with habitual sleep and limit the individual's ability to adhere to the sleep interventions.
9. Unstable psychiatric illness, including the current or past diagnosis of psychotic or bipolar disorder assessed by self-report and/or medical record.
10. Moderate/severe or severe depression. Moderate-severe or severe depression will be assessed with the Patient Health Questionnaire (PHQ-9). Moderate-severe depression or severe depression may contribute to sleep disturbances and interfere with the participant's ability to adhere to the sleep interventions. Therefore, individuals with PHQ-9 scores ≥ 15 will be excluded.
11. Any condition that, in opinion of the PI, will interfere with the safe completion of the study.

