7.1 Study Procedures/Evaluations

7.1.1 Study Specific Procedures

Participants meeting the telephone screen eligibility criteria will be invited to the CTSI. CTSI visit 1 will be scheduled within 4 weeks of the telephone screen. At the CTSI visit 1, participants will provide written informed consent prior to the study specific procedures listed below. All surveys at the CTSI will be completed using REDCap.

- Medical history will be obtained by completing specific surveys at the CTSI visit 1. Surveys will include: Alcohol Use Disorders Identification Test (AUDIT), ARES, Insomnia Severity Index, selected questions from the Sleep Disorder Symptom Checklist -25 , the NINR BRICS with race clarifying questions, Patient Health Questionnaire (PHQ-9), Primary care provider contact information, and a targeted health survey. Prediabetes (HbA1c \geq 5.7% and $<$ 6.5%) will be confirmed from the NYULH medical records (for NYULH participants) or from a HbA1c point of care fingerstick test (for non-NYULH participants).
- Medication history will be obtained by completing specific surveys at the CTSI visit 1. Surveys will include self-reported prescription and over-the counter medications. Specific permitted and prohibited medications will also be queried. Prohibited medications include prescribed medications for T2DM with the exception of Metformin and chronic use of prescribed or over the counter sleep medications (greater than or equal to three times per week).
- Physical examination performed at the CTSI visit will be targeted and include a measured height, waist, and weight, neck circumference, and blood pressure.

CONFIDENTIAL

This material is the property of the NYU School of Medicine and NYU Langone Health. Do not disclose or use except as authorized in writing by the study sponsor
Behavioral Intervention Template Version: 11 January 2019

- Radiographic or other imaging assessments. Not applicable.
- Biological specimen collection and laboratory evaluations. Participants who do not have the results of a HbA1c within the previous 3 months of the CTSI visit 1 will have a Hemoglobin A1c point of care fingerstick to confirm high risk prediabetes. Participants may also be offered the option to provide a blood sample that will be de-identified for future analysis of biomarkers for metabolic disorders, sleep or circadian health, or other health conditions See Section 7.2. All blood draws will take place during the CTSI visit 1.

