10.6 Measures to Minimize Bias

10.6.1 Enrollment/Randomization/Masking Procedures

After the 2-week at-home sleep assessment and baseline data collection, eligible participants will be randomly assigned to the sleep intervention group or to the time and attention matched control intervention group using a block randomization method. Selection bias will be reduced by using random block sizes and keeping the PI blind to the size of each block. Participants will be blinded to the group assignment. It will not be possible to blind the interventionists to the intervention. The study biostatistician will have no direct contact with study participants and will not be blinded to group assignment. The biostatistician will produce and maintain the randomization codes for the blocks. Randomization may only be unmasked by the biostatistician at the completion of analysis of the primary outcome, or for reporting of SAEs or UPs for which it will be essential to provide information to the PI on group assignment.

CONFIDENTIAL

This material is the property of the NYU School of Medicine and NYU Langone Health. Do not disclose or use except as authorized in writing by the study sponsor
Behavioral Intervention Template Version: 11 January 2019

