### **1.3.2 Analysis of the Primary Efficacy Endpoint(s)**

A multivariable Linear regression model was used to assess the effect of the sleep intervention with the subject specific change in the percent time glucose is  $\geq 140$  (Time above target) from baseline as the continuous outcome variable and intervention arm (0=Control Intervention [CI], 1=Sleep Intervention [SI]) as a dichotomous predictor. Effect sizes were presented as beta coefficients and associated 95% confidence intervals, equal to the expected difference between the SI and CI. Important covariates that will be controlled for in these analyses include demographic characteristics including age (continuous), sex (female/male), and race (Asian, Black, White, Other). Statistical significance was determined with a  $p$ -value  $< 0.05$  using a two-tailed test for significance. Normality was assessed using a skewness cutoff of  $\pm 2$ , following established guidelines.

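### Baseline metformin use is recorded before randomisation but is neither a stratification factor nor a prespecified covariate; the cost is chance imbalance and some lost precision, not bias

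*Protocol*

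**What the plan says.** **Eligibility.** Protocol 5.1, criterion 2, accepts an HbA1c of at least 5.7% and below 6.5%, with metformin as an alternative: "or taking Metformin or Glucophage. Individuals with a HbA1c in this range have been identified". Protocol 5.2, criterion 1, excludes insulin and oral hypoglycaemic drugs other than metformin, and gives this reason: "The diagnosis of T2DM and treatment with anti-diabetic agents will confound continuous glucose monitoring assessments". It then makes the exemption: "Individuals taking metformin alone will not be excluded as metformin is frequently prescribed for prediabetes". The reason offered for the exemption is how often the drug is prescribed. Nothing is said about whether it affects CGM. Neither section requires use to have been stable for any period before the baseline CGM week.

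**Data.** Protocol 7.1.1 states: "Medication history will be obtained by completing specific surveys at the CTSI visit 1". It adds: "Specific permitted and prohibited medications will also be queried". Visit 1 is Day 0, and randomisation follows in week 3 (7.3.2, 7.3.3).

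**Design and analysis.** Participants are allocated "using a block randomization method" with random block sizes (10.6.1); no stratification factor is named. The primary outcome is each participant's change from baseline in percent time at or above 140 mg/dL. Protocol 10.4.2 lists age, sex, race/ethnicity, diet quality and physical activity as covariates. SAP 1.3.2 lists "demographic characteristics including age (continuous), sex (female/male), and race (Asian, Black, White, Other" and stops there. Metformin is in neither list. Protocol 10.4.3 carries the same approach over to glucose variability.

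**Contingent adjustment.** Protocol 10.4.6 plans between-arm tests of baseline measures and adjustment for important covariates found to be imbalanced. It names no variable and sets no threshold, and the supplied SAP text does not repeat it.

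**The concern.** The primary endpoint comes entirely from CGM. The protocol gives interference with CGM as its reason for keeping out anti-diabetic drugs, then admits one of them both as an exemption and as a route to eligibility. Protocol 10.4.2 chooses covariates for their association with sleep and glycaemic control. By that test, a permitted glucose-lowering drug is an obvious candidate.

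If metformin users change differently from non-users between the two CGM weeks, two things follow. A chance excess of users in one arm moves this trial's estimate, and the variance explained by metformin stays in the error term. Both are avoidable with a variable already collected before randomisation. Leaving it to 10.4.6 would make its entry into the model depend on the observed data.

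**Working it through.** **1. The plan's own sample size.** Inputs from protocol 10.5: effect 0.6 SD, two-sided alpha 0.05, 95% power. The normal approximation gives 2 × (1.960 + 1.645)² / 0.6² = 72.2, so 73 per arm. The t-test solution is 73.17, so 74, which matches the stated 74. The plan recruits 75 per arm for evaluation, and 75 / 0.8 = 93.75, so 94 per arm and 188 in total, as stated. Power at 75 per arm is 95.5% (t-test). None of these figures is in dispute.

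**2. Assumptions.** The documents do not give the share of participants on metformin (m) or the difference in mean change between users and non-users (g, in SDs of the change score). I take m = 10% to 40% and g = 0.2 to 0.8. Both ranges are illustrative. The true g could be smaller, including zero.

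**3. Chance imbalance without stratification.** The SD of the between-arm difference in the share of users is sqrt(2m(1−m)/75).

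| m | SD of difference | 95% range (± points) | Chance of 10 points or more |
|---|---|---|---|
| 10% | 0.049 | 9.6 | 4% |
| 20% | 0.065 | 12.8 | 13% |
| 30% | 0.075 | 14.7 | 18% |
| 40% | 0.080 | 15.7 | 21% |

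**4. Effect on the estimate and on precision.** The shift at the edge of the 95% range is 1.96 × SD × g. The variance explained is R² = m(1−m)g², with the total SD set to 1. The adjusted SD is sqrt(1−R²), and power uses 0.6 / sqrt(1−R²) at 75 per arm. Each range below runs from m = 10% to m = 40%.

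| g | Shift (SD) | Share of 0.6 SD | R² | n per arm for 95% power (normal; 73 unadjusted) | Power at 75 per arm (95.5% unadjusted) |
|---|---|---|---|---|---|
| 0.2 | 0.02–0.03 | 3–5% | 0.4–1.0% | 72 | 95.5–95.6% |
| 0.5 | 0.05–0.08 | 8–13% | 2.3–6.0% | 71–68 | 95.8–96.5% |
| 0.8 | 0.08–0.13 | 13–21% | 5.8–15.4% | 69–62 | 96.4–97.8% |

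These figures ignore the other covariates and the single degree of freedom spent, which is negligible with 150 participants.

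**5. Scale against sampling error.** The standard error of the arm difference at 75 per arm is sqrt(2/75) = 0.163 SD. The shifts above therefore run from 0.019/0.163 = 0.12 to 0.125/0.163 = 0.77 standard errors. Adjustment narrows the confidence interval by 1 − sqrt(1−R²): 0.2–0.5% at g = 0.2, 1–3% at g = 0.5, and 3–8% at g = 0.8.

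**The case against.** The strongest reply is that nothing is invalid as it stands. Randomisation makes arm and baseline metformin use independent in expectation. The shifts in the working are ordinary sampling variation that the 95% confidence interval already covers. The outcome is a change score, so someone on metformin in both CGM weeks carries the same level effect in both and it cancels. No document supports any particular non-zero g. Protocol 10.4.6 also plans systematic baseline comparisons followed by adjustment. All of this stands, and it limits the point to efficiency and protection against chance imbalance.

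Four stronger readings are tempting, and the documents do not support them.

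- *That the omission biases the result.* Protocol 5.2 speaks of confounding CGM measurements. That is not confounding of a randomised comparison of change.
- *That the protocol itself says metformin confounds CGM.* It gives a general reason about anti-diabetic agents and then exempts metformin. Applying the reason to metformin is a fair inference, but the protocol does not state it.
- *That metformin is the only glycaemia-related factor left out.* The SAP also drops diet quality and physical activity, which protocol 10.4.2 had listed.
- *That the covariate would deal with recent starters.* Someone whose glucose is still moving after starting the drug is a plausible reason for a difference in change. A yes/no variable from visit 1 cannot separate such people from long-term users.

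One part of the reply does not carry. Section 10.4.6 is systematic in its testing, but the choice of adjustment remains driven by the data, with no named variable and no threshold. Fixing the covariate in advance is the better rule.

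**Conclusion.** The point holds as a low-cost improvement. Baseline metformin use is a pre-randomisation variable with a rationale in the protocol's own terms, and no document prespecifies its use in the design or the primary model.

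Under the assumed 10–40% users and 0.2–0.8 SD difference in change, the exposure is a shift of about 0.02–0.13 SD (3–21% of the design effect) at the edge of the 95% chance range. The gain in power from 95.5% is at most about 2.3 percentage points. If users and non-users change alike, both are zero. The planned sample size is unaffected, and no stated error rate or figure is wrong.

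Separately, the two sentences in 5.2 sit uneasily together: the stated reason for exclusion is not reconciled with the exemption. This review takes no position on which eligibility rule is right.

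**What to change.** In protocol 10.4.2 and 10.4.3 and in SAP 1.3.2, name baseline metformin use (yes/no, from the CTSI visit 1 medication history) as a fixed covariate in the primary and secondary models, whatever the observed balance.

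Most of the SAP is written in the past tense. If the primary analysis has already been run, adding the covariate to it would be a post hoc change. In that case, leave the primary model as it is and report the metformin-adjusted model as a clearly labelled sensitivity analysis.

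In 5.2, reconcile the statement about confounding with the metformin exemption.

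The cost is one degree of freedom and a short text change, with no new data and no larger sample. The downside is that the gain may be negligible, and that the covariate does not address recent changes in metformin use.

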5.3 Vulnerable Subjects

Children, pregnant women, fetuses, neonates, the elderly, persons with decisional incapacity, or prisoners are not included in this research study.

Employees and students may be enrolled. They will be informed that their decision to participate will not affect their academic or employment standing. No students who are under the supervisory oversight of the study team members will be enrolled.

CONFIDENTIAL

This material is the property of the NYU School of Medicine and NYU Langone Health. Do not disclose or use except as authorized in writing by the study sponsor
Behavioral Intervention Template Version: 11 January 2019

5.4 Strategies for Recruitment and Retention

We plan to telephone screen 1,000 potential participants to enroll 800 community-dwelling, short sleeping adults (≥ 21 years and < 65) with prediabetes (defined as Hemoglobin A1c $\geq 5.7\%$ and $< 6.5\%$) in order to retain 188 participants who will complete the intervention. Short sleep will be defined as ≤ 6.0 hours of actigraphy-estimated sleep. Based on patients seen at New York University Langone Health (NYULH) diagnosed with prediabetes during the last year ($\text{HbA1c} \geq 5.7\%$ and $< 6.5\%$), we anticipate recruiting a sample consisting of 57% females, 43% males, 46% Whites, 24% Blacks, and 30% other races/ethnicities.

Prior to recruitment, IRB approval will be obtained from the New York University School of Medicine. We will recruit participants from the community by 1) electronically posting study flyers, 2) advertising in the community and via social media 3) posting flyers in clinics, 4) distributing flyers at NYULH facilities, 5) contacting past study participants who agreed to be contacted for future research studies, 6) using Epic to identify and contact potential participants, 7) using research registries such as Research Match, and 8) using a peer recruitment strategy.

All inquiries will be subjected to a structured telephone interview conducted by the project coordinator or research assistant to determine potential eligibility. If the telephone interview indicates that the potential participant may be eligible, s/he will be contacted by the project coordinator to schedule the CTSI visit 1.

1) Electronically-posted flyers: IRB-approved electronic flyers will be posted at selected sites with permission from the site. Potential sites include NYULH, Bellevue Hospital, NYU College of Dentistry, NYU College of Nursing, commuter ferries and ferry terminals, and metro terminals. Interested persons responding to the flyers will be contacted by the project coordinator or research assistant and provided with the option of proceeding with the IRB-approved telephone screening.

2) Advertising in the community: Community members may learn of the study through electronically-posted flyers or other methods, such as radio talk shows (e.g., NYU Langone Nurse Radio, sleep apnea support groups). Interested community members may contact the study team for more information about the study. After contacting the study team, the project coordinator or research assistant will provide individuals with the option of proceeding with the IRB-approved telephone screening.

3) Posted/distributed flyers: Flyers promoting the study will be available to individuals who visit the participating NYULH and Bellevue Hospital health facilities. Flyers will also be distributed at community sites so that interested individuals can contact the study team. Those responding to the distributed flyer will be contacted by the project coordinator or research assistant and provided with the option of proceeding with the IRB-approved telephone screening.

4) NYULH recruitment: This study will recruit individuals from settings affiliated with NYULH, such as employee health, occupational medicine, cardiology, endocrinology, emergency medicine, and college of nursing faculty practices. Flyers promoting this study will be available to individuals who visit the participating health facilities or attend employee health events (e.g. flu shot clinics, health fairs). Clinical staff informed of the study protocol and provided with the IRB-approved study information may also inform individuals about the study and refer them to the study team to contact if interested in participating in the study. With approval of the clinical site, the research staff will also be available at the clinical site during specific hours to facilitate recruitment. However, given the current limitations for being onsite for recruitment, this study will expand recruitment to include telephone or email recruitment of patients seeking care at all NYULH Family Health Centers and other NYULH settings. Working with the Family Health Centers and NYULH staff and scheduling personnel and NYU Langone DataCore personnel, the PI will obtain a list of patients with appointments in the NYU Langone Family Health Centers and other NYULH settings during the next month. This may include viewing the upcoming schedule in Epic. The PI will email the list of potential participants to their providers telling them their patient will be contacted about this study (the patients will be contacted via phone or email). The PI will ask the provider in this email if they have any objections to their patient's participation in the study. If there are no objections, the PI will contact the patient

CONFIDENTIAL

This material is the property of the NYU School of Medicine and NYU Langone Health. Do not disclose or use except as authorized in writing by the study sponsor
Behavioral Intervention Template Version: 11 January 2019

telling them about the study. Patient's that do not have a primary care provider or other health care provider identified will be contacted via phone or email.

5) Past study participants. Only past study participants from the PI's and Co-I's previous studies who agreed to be contacted for future studies will be contacted by the project coordinator or research assistant. Contacted individuals expressing interest in the study will be provided with the option of proceeding with the IRB-approved telephone screening.

6) DataCore/Epic. See below.

7) Research Match. We will also utilize Research Match (ResearchMatch.org), a national, electronic, web-based recruitment tool that was created through the Clinical and Translational Science Awards Consortium in 2009 and iConnect to send study recruitment messages to potential study participants. This study's recruitment content will be inserted into the standard Research Match electronic notification that informs possible matched participants that they have been identified as a potential match for this study. The secure Research Match clearinghouse will route an IRB approved Research Match notification to each of these Research Match participants. These potentially matching participants will have the option of replying "yes", "no", or "not respond" through a set of quick links available in this notification of the study announcement. The contact information of the "yes" responding participants will be made available on the PI's "Manage my Study" dashboard. A member of the research team will contact the individual who expresses interest. If a subject requests information regarding opting out of further recruitment for all research, subjects will be directed to contact the study coordinator or have subjects contact [contact] or [name].

8) Peer recruitment strategy. This study will employ a hybrid sampling strategy involving targeted sampling from recruitment venues and peer recruitment. Initial seeds who are selected by study staff to recruit peers to the study, and individuals who were recruited by peers. They will be asked to recruit peers who they know by name or face, and are living with pre-diabetes. They will receive \$10 for each peer who completes the CTSI screening visit.

Written informed consent will take place during the first clinic visit at the CTSI prior to any study related procedures. At the CTSI visit 1, the study details and procedures will be discussed with the project coordinator. The potential participant will be given adequate time to ask questions and review the informed consent document. Once satisfied that all questions have been answered, the potential participant will either decline to participate or sign the informed consent document. The consent form will be signed in the presence of the project coordinator. All participants must read, sign, and date a consent form before entering the study, undergoing physical examination, or undergoing any testing.

Participation retention will be enhanced by scheduling and reminding participants about weekly intervention visits, tracking the completion of daily sleep diaries, and sending email reminders if the daily sleep diary has not been completed. The study team will reach out to participants as needed to problem solve for missed sessions or missing sleep diaries.

